5.1.1 Atopic dermatitis patients

Age

I 01. Male or female of ≥ 18 years of age inclusive, at the time of signing the informed consent form (ICF).

Type of participant and disease characteristics

I 02. Diagnosed with moderate-to-severe chronic AD for at least 1 year before screening.

I 03. Eligible to be treated with dupilumab according to product monograph.

I 04. Pruritus lasting 6 or more weeks before baseline (Day 1).

I 05. Eczema Area and Severity Index (EASI) score ≥ 12 at baseline.

I 06. Pruritus numerical rating scale (NRS) ≥ 4 at baseline.

I 07. Investigator global assessment (IGA) score of ≥ 3 at screening (on the 0 to 4 scale) at baseline.

I 08. Atopic dermatitis active lesions on the upper limbs or lower limbs suitable for a skin biopsy without oozing, bleeding, or infection on upper limbs or trunk.

I 09. Patients with acute AD lesions as determined by Investigator's judgment.

I 10. Participants able to accept skin biopsy procedure.

- I 11. Participants willing to refrain from applying any emollients or topical medications on the target assessment areas (including lesional and non-lesional) throughout the study unless necessary to treat intolerable symptoms.
- I 12. Participants willing and able to comply with all site visit and study-related procedures.
- I 13. Participants able to understand and complete all patient related outcome assessments and questionnaires.

Concomitant medication

- I 14. Stable treatment with non-prohibited medication ([Section 6.5.2](#)) or therapy during the study.

Informed consent

- I 15. Capable of giving signed informed consent which includes compliance with the requirements and restrictions listed in the ICF and in this protocol. In countries where legal age of majority is above 18 years, a specific ICF must also be signed by the participant's legally authorized representative.

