6.5.1 Rescue medicine

During Treatment Period, if medically necessary (ie, to control intolerable AD symptoms on face and genital areas), rescue treatment for AD may be provided to participants at the discretion of the Investigator (ie, topical treatment with high potency topical corticosteroids [TCS]). Investigators should make every attempt to conduct efficacy and safety assessments (eg, disease severity scores, safety laboratory assessments) immediately before administering any rescue treatment. An unscheduled visit may be used for this, if necessary.

Investigators will be required to perform an IGA evaluation prior to starting rescue treatment and initiate rescue treatment only in patients who either have an IGA score of 4, or have intolerable AD symptoms. The date and time of rescue medication administration as well as the name and dosage regimen of the rescue medication must be recorded in the eCRF.

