9.3 POPULATIONS FOR ANALYSES

The following populations are defined ([Table 3](#)):

Table 3 - Populations for analyses

| Population | Description |
|-----------------------|--|
| Enrolled | All participants who sign the ICF |
| Intent-to-treat (ITT) | All enrolled patients, who received at least 1 dose of IMP and all enrolled healthy participants who have at least 1 skin biopsy performed, irrespective of compliance with the study protocol and procedures. |

| Population | Description |
|---------------------|---|
| Modified ITT (mITT) | All ITT participants. If prohibited therapies for AD (see Section 6.5.3) are used and assessed by the study team as having a significant impact on skin biopsy assessment, only visits prior to rescue treatment use are considered. |
| Safety | The safety population includes all patients, who actually received at least 1 dose of IMP or had at least 1 skin biopsy and all healthy participants who had a skin biopsy or another safety assessment performed |

Abbreviations: AD: atopic dermatitis, ICF: informed consent form; IMP: investigational medicinal product; ITT=intent-to-treat, mITT: modified ITT.

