9.4.6 Efficacy analyses

The efficacy evaluation will be based upon the review of the individual values (graphics), descriptive statistics (summary tables, graphics) and, where applicable, exploratory statistical analysis.

Due to the small sample size and the exploratory nature of the study, missing, or incomplete data of efficacy marker will not be imputed. In case a significant number of patients (eg, more than 20%) using rescue therapy are observed during the study Treatment Period, visit values removed due to use of rescue therapy will be imputed. The imputation methods applied will be described in the SAP.

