9.4.7 Description of efficacy variables

Efficacy parameters are described in [Section 8.1](#). The derivation of baseline results is described in [Section 9.4.3.2](#).

The analysis of the efficacy markers will be based on the mITT population. As a sensitivity analysis, the primary endpoint will also be analyzed based on the intent-to-treat (ITT) population. Secondary endpoints analysis might be run on the ITT population as sensitivity analysis in case an important number of patients using rescue therapy is observed.

Sub-group analyses might be done, if deemed appropriate.

If relevant, based on results obtained on planned analyses (eg, if any trend or signal is observed), further exploratory analyses could be conducted, using statistical models for instance.

Analysis

Table 4 - Efficacy analyses

| Endpoint | Statistical analysis methods |
|------------------|--|
| Primary | 
Change from baseline on Week 17 for intraepidermal nerve fiber density by PGP9.5 antibody staining in lesional skinChange from baseline on Week 17 for intraepidermal nerve fiber branching by PGP9.5 antibody staining in lesional skinRaw data and change from baseline to Week 17; ie, absolute and percent changes, will be summarized with descriptive statistics (such as mean, median, SD, minimum, maximum, and 90% confidence interval) and plots for AD participants based on the mITT population |

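### Itch scores after rescue stay in the mITT responder rate unless the rescue is judged to affect the biopsy, and no planned table shows response without rescue

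*Protocol*

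**What the plan says.** Protocol Section 9.3, Table 3, takes all ITT participants into the mITT set and adds one restriction. It opens "If prohibited therapies for AD (see Section 6.5.3) are used" and continues that, where this use is "assessed by the study team as having a significant impact on skin biopsy assessment, only visits prior to rescue treatment use are considered". Two conditions must therefore both be met: a prohibited therapy was used, and the study team sees a significant effect on the biopsy read-out. When the rule applies, it cuts whole visits, so the clinical and patient-reported values of those visits go too.

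Section 9.4.7 applies this set throughout: "The analysis of the efficacy markers will be based on the mITT population". Table 4 repeats it for the proportion with at least 4 points of improvement in peak pruritus NRS at Weeks 3, 5, 9, 17 and 21. On the ITT set, "Secondary endpoints analysis might be run on the ITT population as sensitivity analysis" if rescue use turns out to be important.

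Section 6.5.1 permits rescue in the Treatment Period, for example "to control intolerable AD symptoms on face and genital areas", with high-potency topical corticosteroids as the named treatment. Footnote e of the AD schedule (Section 1.3) prefers the forearms, then the back, for biopsy.

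Section 9.4.6 says: "In case a significant number of patients (eg, more than 20%) using rescue therapy are observed" in the Treatment Period, "visit values removed due to use of rescue therapy will be imputed", with methods to follow in the SAP. SAP 1.2.6 plans no imputation for efficacy. SAP 1.2.5 adds a listing of rescue medications.

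**The concern.** A test about biopsy tissue decides which itch scores count. Nothing in the plan asks whether a treatment could have changed itch or clinical severity. Rescue that spares the biopsy site passes through, even when it relieves the symptom being measured.

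The study has a single arm, so no control group shares the effect of rescue. Response is measured only against the participant's own baseline, and any relief from a corticosteroid is read as relief from dupilumab. The itch response is a named secondary endpoint. Section 2.2 also makes it a purpose of the study to relate neuronal change to itch improvement, and itch relief obtained away from the biopsy site could blur that relation.

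Nothing here concerns type I error, since no hypothesis is tested, or the primary nerve fiber endpoints, for which a biopsy-based rule is sensible.

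**Working it through.** No figure in the plan underlies this point, so the check is mainly a reading of the text, followed by simple arithmetic on size.

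**1. Is there any other removal rule?**
- Section 9.4.6 speaks of values removed because of rescue, but contains no rule that removes them. It only says what happens to them afterwards.
- Section 9.4.7 offers an optional ITT run, which keeps every post-rescue value.
- SAP 1.2.6 imputes nothing.
- SAP 1.2.5 produces a medication table and a rescue listing, not a response table.

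Table 3 is therefore the only rule, and its trigger is biopsy impact.

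**2. Would permitted rescue meet that trigger?** Rescue is foreseen for face and genital areas (Section 6.5.1), and biopsies are taken preferably from forearm or back (Section 1.3, footnote e). With treatment and biopsy at different sites, a finding of significant biopsy impact would be unusual, though the study team could still make one.

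**3. What happens to the itch value?** If the trigger is not met, the visit stays in mITT. Table 4 then counts a 4-point improvement with no condition on rescue.

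**4. Size per participant.**
- Planned AD participants: 34 (Section 9.2).
- Drop-out allowance: 20% (Section 9.2), so 34 × 0.8 = 27.2, taken as 27.
- If k participants are responders only because of rescue, the response rate is too high by k/n.

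| k (assumed) | n = 34 | n = 27 |
|---|---|---|
| 0 | 0 | 0 |
| 1 | 1/34 = 2.9 points | 1/27 = 3.7 points |
| 3 | 3/34 = 8.8 points | 3/27 = 11.1 points |
| 6 | 6/34 = 17.6 points | 6/27 = 22.2 points |

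The values of k are assumptions, because the documents give neither a rescue rate nor a response rate. As an illustration, with an assumed 17 of 34 responders as observed (50.0%) and k = 3, the rate with rescued participants as non-responders is 14/34 = 41.2%.

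**5. EASI for comparison.** Under SAP 1.2.6.2 the head and neck region can contribute at most 0.1 × 12 × 6 = 7.2 of 72 points. Facial rescue can therefore move the mean by at most 7.2/34 = 0.21 points per participant. The itch responder rate is the more exposed endpoint.

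**6. The cross-reference.** Table 3 points to Section 6.5.3 for prohibited therapies. That section covers permitted medications; the prohibited list is in 6.5.2.

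**The case against.** The best defence is that as-observed reporting is a legitimate choice in a small, descriptive, exploratory study. Individual data are listed by participant with relative day (SAP 1.3). With the rescue listing, a reader could count response without rescue by hand for 34 people. Section 9.4.7 leaves room for subgroup and further exploratory analyses, and Section 9.4.2 has prohibited therapies reviewed before database lock. Peak pruritus NRS asks for the worst itch overall, not by body site (Section 8.1.1.1), so facial or genital treatment lowers it only if that site drove the worst itch. All of this stands. It limits the weight of the point but does not supply the missing table.

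Several stronger readings are tempting, and the documents do not support them:
- A reader might take the 20% in Section 9.4.6 as a ceiling and infer a maximum distortion of 6/34 = 17.6 points, since 7/34 = 20.6% passes it. The figure is an example that triggers imputation of removed values. It does not limit rescue use.
- A reader might infer that antihistamines for itch enter through the exception in Section 6.5. That exception requires that the drug not interfere with the study, which one that lowers itch scores would fail. Such use would be a deviation. Table 3 cuts at rescue use, so it is unclear whether a non-rescue drug could trigger removal at all.
- A reader might infer that rescue is allowed in Weeks 17 to 21, because criterion I 11 bars topical products "throughout the study unless necessary to treat intolerable symptoms". That criterion concerns the target assessment areas, where the biopsy rule may well apply. In follow-up, prohibited treatment is again a deviation.
- A reader might cite the responder paragraph in SAP 1.2.6.2. Read literally, it applies to the sleep, pain, sensitivity and burning scales at a different set of weeks. The itch argument rests on Protocol Table 4.

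**Conclusion.** The point holds for the peak pruritus response: post-rescue values stay in as observed whenever the study team finds no significant biopsy impact, and no planned table shows response without rescue. Retention is not automatic, since a finding of biopsy impact would remove the later visits for every endpoint. Section 9.4.6 suggests that wider removal was intended, but no rule carries it out.

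The size is 2.9 to 3.7 percentage points for each participant who responds only because of rescue. This assumes a denominator between 34 and 27 and that the treatment alone produced the 4-point change. The total is unknown and may be zero. The wrong section reference is clerical and, on its own, changes no result. The change below is worth considering; the plan is not unsound without it.

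**What to change.** 1. In Protocol Table 3, change the reference for prohibited therapies from Section 6.5.3 to 6.5.2.
2. In SAP 1.2.6.2, keep the as-observed peak pruritus responder table (Weeks 3, 5, 9, 17 and 21). Add beside it one sensitivity table that counts a participant as a non-responder at visits after the start of rescue therapy, or of any other Section 6.5.2 treatment recorded as given for AD or itch. If nobody qualifies, say so and omit the table.

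A companion table that carries the last pre-rescue EASI, SCORAD and patient-reported scores forward is not recommended. Rescue starts at IGA 4 or with intolerable symptoms, so it would freeze flare values, possibly for much of the treatment period. It would also depart from SAP 1.2.6.

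The cost is one corrected reference and one extra table, from dates and reasons for use that Sections 6.5 and 6.5.1 already require. SAP 1.2.5 identifies rescue by a single coded reason, so other treatments need a short review of the recorded reason before database lock. Response rates in the sensitivity table will be somewhat lower if rescue occurred. A brief early course counts against the participant at all later visits, which is conservative; this is why the two tables should stand side by side.

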5.4 SCREEN FAILURES

Screen failures are defined as participants who consent to participate in the clinical study but are subsequently found to be not eligible to enroll in the study. A minimal set of screen failure information is required to ensure transparent reporting of screen failure participants to meet the Consolidated Standards of Reporting Trials (CONSORT) publishing requirements and to respond to queries from regulatory authorities. Minimal information includes demography, screen failure reasons, eligibility criteria, and any serious AE (SAE).

Note: “Enrolled” means a participant’s, or their legally acceptable representative’s, agreement to participate in a clinical study following completion of the informed consent process. Potential participants who are screened for the purpose of determining eligibility for the study, but do not participate in the study, are not considered enrolled, unless otherwise specified by the protocol.

Rescreening may be allowed once during the open screening period and upon the Investigator’s decision (for certain circumstances, eg, participants cannot start the study due to private reasons). All screening procedures will have to be repeated and a different patient identification number will be assigned. There is no requirement for a waiting period between the screen failure date and the rescreening date. Participants who are rescreened must sign a new consent form and all Visit 1 procedures must be repeated.

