8.3.1 Skin biopsy samples

Skin biopsies of 4 mm diameter each will be collected from healthy participants and AD participants at time points according to the SoA ([Section 1.3](#)). Study staff will provide instructions regarding suture removal, if sutures are used for closure.

Gelfoam®, a hemostatic, can be applied for biopsy closure. Study staff will notify the patient this will dissolve and provide instructions regarding wound dressing and care.

The skin biopsy samples will serve to study the neuronal architecture (neuroanatomy) and neuromarkers in the epidermis of pruritic lesional skin before start of treatment with dupilumab and localisation matched post-lesional healing skin areas after EoT with dupilumab in AD participants. Accordingly, the collection of 4 biopsies in total is mandatory for AD participants at the following timepoints:

- Baseline: 2 biopsies of 4 mm diameter each at baseline before start of treatment from pruritic lesional skin.
- Week 17: 2 biopsies of 4 mm diameter each from non-pruritic, post-lesional healed or healing skin, with localisation matched to the baseline pruritic lesional biopsy.
 - if post-lesional healed skin that is completely non-pruritic non-lesional is not available at later visits, one of the following biopsies should be collected (in the order of relevance): 1. lesional non-pruritic skin, 2. Post-lesional pruritic skin or 3. lesional pruritic skin.

Participants who refrain from providing these biopsies at baseline and Week 17 are not eligible for this study.

Collection of the following additional biopsies is optional for AD patients, including

- 2 biopsies of 4 mm diameter each from non-pruritic, post-lesional healed or healing skin, localisation matched to the baseline pruritic lesional biopsy, at week 3 and at the end of the observation period at Week 21.
 - if post-lesional healed skin that is completely non-pruritic non-lesional is not available at later visits, one of the following biopsies should be collected (in the order of relevance): 1. lesional non-pruritic skin, 2. Post-lesional pruritic skin or 3. lesional pruritic skin.
- 2 biopsies of 4 mm diameter each from *non-lesional skin* at baseline.

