9.4.4 Extent of study treatment exposure and compliance

The extent of study treatment exposure and compliance will be assessed and summarized for patient group within the safety population.

The following listings will be provided:

- Patients receiving IMP from specified batch; (patient, IMP, and IMP batch number) will be sorted by patient.

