9.4.8.1 Adverse events

9.4.8.1.1 Definitions

Adverse events will be coded to a "Preferred Term (PT)" and "High Level Group Term (HLGT)", "High Level Term (HLT)" and primary "System Organ Class (SOC)" using the Medical Dictionary for Regulatory Activities (MedDRA, version currently in use by the Sponsor at the time of database lock).

For AD participants' group, they will be classified into predefined standard categories according to chronological criteria:

- Pre-treatment AEs: AEs that occurred, worsened or became serious during the pre-treatment period defined as the time between informed consent signature and the first IMP administration.
- Treatment-emergent AEs (TEAEs): AEs that occurred, worsened or became serious during the TEAE period defined as the time from the first IMP administration up to the EoT Visit (EoT included).
- Post-TEAEs: AEs that occurred, worsened or became serious during the post-TEAE period defined as the time starting after the TEAE period (including the follow-up period).

Treatment-emergent AEs will be assigned to the treatment received at the time of the AE onset.

If the onset date (or time) of an AE (occurrence, worsening or becoming serious) is incomplete or missing, then the AE will be considered as a TEAE unless a partial date (or time) shows it as a pre- or post-treatment event.

For all healthy participants, safety data will be considered as part of a single period starting with the signature of the informed consent and ending with the EoS Visit (EoS included).

All AEs reported in the study will be listed, sorted by participant, onset date and time.

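### TEAE and AESI percentages are planned on a safety population that can include AD patients who were biopsied but never dosed

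*Protocol*

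**What the plan says.** Protocol Section 9.3, Table 3, defines the AD part of the safety population as "all patients, who actually received at least 1 dose of IMP or had at least 1 skin biopsy". Either condition is enough. The ITT row of the same table is narrower for patients: "All enrolled patients, who received at least 1 dose of IMP". The clause that widens the safety population beyond dosed patients also covers the healthy participants: "or had at least 1 skin biopsy and all healthy participants who had a skin biopsy or another safety assessment performed".

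Section 9.4.8 places all safety analyses on this population. Section 9.4.8.1.1 makes the TEAE period for AD participants "defined as the time from the first IMP administration up to the EoT Visit (EoT included". Section 9.4.8.1.2 reports the number and percentage of patients with TEAEs for the AD group of the safety population, and Section 9.4.8.1.5 gives AESI counts and percentages. Section 9.4.4 says that exposure and compliance "will be assessed and summarized for patient group within the safety population".

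On sequence, Section 8.3.1 requires "2 biopsies of 4 mm diameter each at baseline before start of treatment from pruritic lesional skin", and footnote a of the Schedule of Activities (Section 1.3) puts all Visit 2 assessments before the first dose.

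SAP Section 1.2 lists the changes to the protocol's statistical section. None touches the safety population. SAP Section 1.2.1 again starts the treatment-emergent period at administration of study drug. For healthy participants it splits observation into a screening segment and a 7-day segment after the biopsy.

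**The concern.** A percentage is interpretable when everyone in the denominator could have contributed to the numerator. The words that admit biopsied patients add an AD patient only if that patient was biopsied and never dosed, because all the others already qualify through their dose. Such a patient has no TEAE period but is counted in the TEAE denominator.

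The sequence makes this possible. Biopsy and first dose fall at the same visit, with the biopsy first. Eligibility is checked again that day, and the pregnancy test is repeated (Section 1.3). A patient could also simply decline to go on after the biopsy.

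TEAE incidence is the only endpoint under the secondary safety objective (Table 1). The error runs in one direction: it makes the drug look slightly safer than it was in those who received it.

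**Working it through.** The documents give no TEAE rate and no expected size for the safety population, so there is no planned figure to reproduce. The check compares the population with the event window and then sizes the effect.

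**Population against event window**

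| AD patient | In safety population (Table 3) | Has a TEAE period (9.4.8.1.1) | In TEAE denominator (9.4.8.1.2) |
|---|---|---|---|
| Biopsied and dosed | yes | yes | yes |
| Biopsied, never dosed | yes | no | yes |

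The second row is the defect. There is one narrow exception. Section 9.4.8.1.1 and SAP Section 1.3 count an AE with missing onset as a TEAE by default, so an undosed patient's undated event could be counted as one.

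**Size**

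Inputs: 34 AD participants (Synopsis; Section 5). Assumed, because the documents give neither: u = 0 to 3 patients biopsied but never dosed, and a true TEAE rate p of 30% to 70% among dosed patients.

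If the u patients are among the 34, the reported rate = p × (34 − u)/34. The relative shortfall is u/34, and 1/34 = 2.9% per patient.

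| u | p = 30% | p = 50% | p = 70% |
|---|---|---|---|
| 0 | 30.0% | 50.0% | 70.0% |
| 1 | 29.1% | 48.5% | 67.9% |
| 2 | 28.2% | 47.1% | 65.9% |
| 3 | 27.4% | 45.6% | 63.8% |

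The shortfall is 0.9 to 2.1 percentage points for u = 1 and 2.6 to 6.2 points for u = 3.

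If instead 34 are dosed and the u patients come on top, the reported rate = p × 34/(34 + u). At p = 50% this gives 48.6%, 47.2% and 45.9% for u = 1, 2 and 3, which is nearly the same.

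For scale, the 95% half-width of a proportion near 50% in 34 patients is 1.96 × √(0.5 × 0.5/34) = 16.8 points. The bias is well inside sampling error.

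**Healthy participants**

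Assume 2 of 10 biopsied volunteers have an AE, which is 20.0%. Add two volunteers who were only screened. The result is 2/12 = 16.7% if neither has an AE and 3/12 = 25.0% if one does. The direction is not fixed, so the AD argument does not carry over.

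**The case against.** The strongest reply is that the case may never arise. Biopsy and first dose share a visit, and the Synopsis says that the 34 will be enrolled and treated. The study is descriptive with no hypothesis tests (Section 9.1), and a shift of one or two points changes no decision. Keeping biopsied patients in a safety set is also defensible, because the punch biopsy is an invasive study procedure with its own stated risks (Section 2.3.2). All of this stands. It limits the size of the problem but does not make the TEAE denominator right.

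A reader might infer three stronger things, which the documents do not support.

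- **That healthy volunteers who were only screened dilute a rate they could not contribute to.** Section 5.4 says "Screen failures are defined as participants who consent to participate in the clinical study but are subsequently found to be not eligible", and examination, serology and IgE at screening (Section 1.4) could bring such volunteers into the set. But healthy safety data form one period from consent to the end-of-study visit (Section 9.4.8.1.1), and AEs are collected from consent (Section 8.5.1). They can have a countable AE. No TEAE table is planned for this group and no percentage is specified. What remains is narrower: they cannot have a biopsy complication and have no time in the SAP's 7-day post-biopsy segment.
- **That exposure and compliance are diluted.** Exposure needs a first and a last dose date (Section 9.4.4.1), and compliance counts administrations planned up to the last dose (Section 9.4.4.2). Without a dose both are undefined, so no value enters the summary.
- **That the safety-set definition turns biopsy complications into TEAEs.** They count because the TEAE definition goes by timing, whatever the cause. Restricting the set to dosed patients would leave those events in.

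**Conclusion.** The point holds for the AD arm only. As written, the plan puts any biopsied but undosed AD patient into the TEAE and AESI denominators with no TEAE period, and the SAP leaves that in place. Incidence is understated by about 2.9% in relative terms per such patient among 34, and not at all if there are none. The mismatch follows directly from the text. Its size rests on assumed counts of 1 to 3 and assumed rates of 30% to 70%, for which the documents offer no evidence. This is a minor clarification worth making because it costs almost nothing. It does not threaten the trial's safety conclusions.

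**What to change.** In Table 3 or the SAP, state that TEAE, AESI, TEAE-period vital-sign, exposure and compliance summaries use AD patients who received at least one dose of study drug. For exposure and compliance this only names the set in which the quantities are defined.

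Keep the dosed-or-biopsied set for all-AE and procedure-related AE summaries and listings, so that events in an undosed patient are still reported.

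For healthy participants, use those with a study biopsy as the denominator of any AE summary for the SAP's 7-day post-biopsy period. List AEs of screened-only volunteers separately.

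The cost is one clause in the text and one extra denominator to track. No new data are needed. The reported TEAE percentage may come out slightly higher.
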